
10. Bone marrow aspirate and biopsy with cytogenetic analysis and iron stains will be performed pre-study, and after 16 weeks of study treatment, and at the time of final response analysis. Additional biological studies obtained with bone marrow aspiration
					

are summarized in Section 14.

11. Every 3 months if patient is < 2 years from study entry, every 6 months if patient is 2-5 years from study entry, every 12 months if patient is 5-10 years from study entry. No specific requirements if patient is more than 10 years from study entry.

12. Only for patients receiving 300 mg eltrombopag dose or higher, resting 12-lead ECG will be obtained pre-dose on Day 1. A post-dose ECG should be obtained at Tmax (3 hours); if assessment cannot be performed at 3 hours, record actual time ECG was performed within a 2-6 hour window post-dose. A pre- and post-dose ECG as described above is required Week 2, week 4, 8 and 16.

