The pharmacokinetics of eltrombopag has been studied after administration of eltrombopag to adult subjects with liver cirrhosis (hepatic impairment). Following the administration of a single 50 mg dose, the $AUC_{0-\infty}$ of eltrombopag was increased by 41 % (90 % CI: 13 % decrease, 128 % increase) in subjects with mild hepatic impairment, 93 % (90 % CI: 19 %, 213 %) in subjects with moderate hepatic impairment, and 80 % (90 % CI: 11 %, 192 %) in subjects with severe hepatic impairment compared with healthy volunteers. There was substantial variability and significant overlap in exposures between subjects with hepatic impairment and healthy volunteers. The influence of hepatic impairment on the pharmacokinetics of eltrombopag following repeat administration was evaluated using a population pharmacokinetic analysis in 28 healthy adults and 79

patients with chronic liver disease. Based on estimates from the population pharmacokinetic analysis, patients with liver cirrhosis (hepatic impairment) had higher plasma eltrombopag AUC(0- τ) values as compared to healthy volunteers, and AUC(0- τ) increased with increasing Child-Pugh score. Compared to healthy volunteers, patients with mild hepatic impairment had approximately 87 % to 110 % higher plasma eltrombopag AUC(0- τ) values and patients with moderate hepatic impairment had approximately 141 % to 240 % higher plasma eltrombopag AUC(0- τ) values. Patients with liver cirrhosis (hepatic impairment) should use eltrombopag with caution and close monitoring.

Race

The influence of East Asian ethnicity on the pharmacokinetics of eltrombopag was evaluated using a population pharmacokinetic analysis in 111 healthy adults (31 East Asians) and 88 patients with ITP (18 East Asians). Based on estimates from the population pharmacokinetic analysis, East Asian (i.e. Japanese, Chinese, Taiwanese and Korean) ITP patients had approximately 87 % higher plasma eltrombopag AUC(0- τ) values as compared to non-East Asian patients who were predominantly Caucasian, without adjustment for body weight differences.

Gender

The influence of gender on the pharmacokinetics of eltrombopag was evaluated using a population pharmacokinetic analysis in 111 healthy adults (14 females) and 88 patients with ITP (57 females). Based on estimates from the population pharmacokinetic analysis, female ITP patients had approximately 50 % higher plasma eltrombopag AUC(0- τ) as compared to male patients, without adjustment for body weight differences.

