Endocrine	Hyperthyroidism or hypothyroidism	
 Interrupt CC-5013 (lenalidomide) and initiate appropriate medical therapy. Resume CC-5013 (lenalidomide) at investigator's discretion (maintain dose level).
Cardiac Arrhythmias	Sinus bradycardia/other cardiac arrhythmia Grade 2	
 Hold (interrupt) dose. Follow at least weekly. If the toxicity resolves to \leq grade 1 resume at next lower dose level.
	\geq Grade 3	
 Discontinue CC-5013 (lenalidomide) study drug.
Other Toxicity	Other non-hematologic toxicity assessed as CC-5013 (lenalidomide)-related \geq Grade 3	
 Hold (interrupt) dose. Follow at least weekly. If the toxicity resolves to \leq grade 2 resume at next lower dose level.

[figure not shown]
Dosing for Eltrombopag

Patients will initially be started on 100 mg eltrombopag (50 mg for subjects of East Asian heritage). Thereafter, dependent on the platelet response (see Table 3 below), the dose of study medication can be increased every 2 weeks, up to a maximum dose of 300 mg/day (150 mg/day for subjects of East Asian heritage).

Modified dosing for subjects of East Asian heritage (i.e., Japanese, Chinese, Taiwanese and Korean) has been implemented for the following reasons. In healthy Japanese subjects, plasma eltrombopag AUC(0- τ) was approximately 80% higher when compared to non-Japanese healthy subjects who were predominantly Caucasian. Similarly, in patients with ITP, plasma eltrombopag exposure was approximately 70% higher in East Asian (i.e., Japanese, Chinese, Taiwanese and Korean) subjects as compared to non-East Asian subjects who were predominantly Caucasian.

Intra-individual dose adjustments will be made in a stepwise fashion, by sequentially increasing to dose levels of 100 mg, 200 mg or 300 mg as needed (50, 100, 150 mg for subjects of East Asian heritage). Titration of study medication with different dosages on different days will be permitted where needed in order to maintain a stable platelet count in the safe range without exceeding platelet counts >400 Gi/L. The dosing regimen of eltrombopag must be individualized based on platelet counts. Use the lowest effective dosing regimen to maintain platelet response.

Figure 4: Schema of dose adjustments for eltrombopag

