Eltrombopag must be taken either in a fasted state (i.e., 1 hour before or 2 hours after food) or taken with food low in calcium (no dairy products). There must be at least a 4-hour interval between eltrombopag and other medications, food, or supplements containing polyvalent cations such as iron, calcium, aluminum, magnesium, selenium, and zinc, including dairy products. After any eltrombopag dose adjustment, monitor platelet counts at least weekly for 2-3 weeks.

At eltrombopag dose levels 200 mg and above, subjects who have discontinued other drugs known to prolong QT and who still have a QTc >480 msec will be excluded

Table 2: Guidelines for Eltrombopag Dose Adjustments

Platelet Counts	Dose Adjustments
No platelet response	
Increase daily dose to the next dose level
 
If platelet counts do not stabilize at desired levels, consider dosing regimens such as different dose levels on alternating days.
 
Wait for 2 weeks to see the effect of the dose increase on platelet response before another dose increase is considered.

200-400 k/uL	
If no post-baseline BM examination has been performed:
 
Decrease daily dose considering dosing regimens such as different dose levels on alternating days.
 
If platelet counts remain between 200-400 k/uL, wait for 2 weeks to see the effect of the dose decrease on platelet response before another dose decrease is considered.

	
If BM blasts have decreased:
 
Maintain dose level and monitor platelet counts weekly.

	
If BM blasts have increased:
 
Decrease daily dose considering dosing regimens such as different dose levels on alternating days.
 
If platelet counts remain between 200-400 k/uL, wait for 2 weeks to see the effect of the dose decrease on platelet response before another dose decrease is considered

>400k/uL	Interrupt treatment and monitor platelets twice a week until platelet counts fall below 150 k/uL and restart treatment by reducing the daily dose to the next dose level considering dosing regimens such as different dose levels on alternating days.
----------	---

During eltrombopag therapy, CBCs, including platelet count and peripheral blood smears, should be assessed weekly until a stable platelet count has been achieved. CBCs including platelet counts and peripheral blood smears, should be obtained monthly thereafter. Blasts will be monitored as indicated in flowchart:

Algorithm for Blast Count Monitoring

[figure not shown]

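### The QTc >480 msec exclusion and the on-treatment ECG schedule start at eltrombopag doses that East Asian subjects, capped at 150 mg, can never reach

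*Combined protocol and SAP*

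**What the plan says.** Section 8.1.2 (Dosing for Eltrombopag) sets doses on two scales. Dosing moves through "dose levels of 100 mg, 200 mg or 300 mg as needed (50, 100, 150 mg for subjects of East Asian heritage"), "up to a maximum dose of 300 mg/day (150 mg/day for subjects of East Asian heritage"). The synopsis repeats the 150 mg cap under Arm A. The reason given is higher exposure: in ITP patients, "plasma eltrombopag exposure was approximately 70% higher in East Asian" subjects, and about 80% higher in healthy Japanese subjects. Section 5.2.2 (Race) reports about 87% in ITP patients, "as compared to non-East Asian patients who were predominantly Caucasian, without adjustment for body weight differences".

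Two QTc provisions carry a dose trigger:

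- Section 8.1.2, just before the dose-adjustment table: "At eltrombopag dose levels 200 mg and above, subjects who have discontinued other drugs known to prolong QT and who still have a QTc" above 480 msec are excluded.
- Section 2, footnote 12: "Only for patients receiving 300 mg eltrombopag dose or higher, resting 12-lead ECG will be obtained pre-dose on Day 1". It then adds a post-dose reading and says: "A pre- and post-dose ECG as described above is required Week 2, week 4, 8 and 16".

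Neither trigger gives an East Asian value, and no other section rescales them.

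Other QTc-related provisions have no eltrombopag dose condition. They are the screening ECG (Section 2), the entry limit of 450 msec for men and 470 msec for women (Section 6.2), discontinuation at QTc >500 or QT >600 msec (Section 8.3), and discontinuation on the investigator's judgment of an adverse event (Section 8.3).

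**The concern.** The protocol treats the upper eltrombopag steps as needing extra QTc protection, but fixes where that protection starts in milligrams of the standard scale only. A subject on the halved scale can reach the top step without meeting either trigger. Sites could apply the 480 msec rule to East Asian subjects from 100 mg, from 150 mg, or not at all, and the text does not settle which.

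Safety and tolerability is a primary objective (Section 4.1.1). QTc prolongation is on the lenalidomide list of possibly related events (Section 9.1), and Section 5.1 has both drugs given together in later cycles. QTc data on treatment are therefore of interest beyond eltrombopag alone. Leaving one subgroup out would affect both patient protection and the completeness of the safety data.

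**Working it through.** The plan gives no figure to reproduce here. The check compares the dose ladders with the triggers, then looks at exposure.

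**1. Literal reading.** The East Asian maximum is 150 mg/day. Since 150 < 200 and 150 < 300, neither trigger is met at any permitted dose. Alternating different doses from day to day cannot change this, because each stays at or below 150 mg.

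**2. What still applies after entry.** In the Section 2 ECG row, the only entry after screening is the one governed by footnote 12. East Asian subjects therefore have no scheduled on-treatment ECG, and the Section 8.3 stop at QTc >500 msec could be met only on an unscheduled one. The "Sinus bradycardia/other cardiac arrhythmia" row in the lenalidomide table might be applied to a prolonged QTc, but it acts on lenalidomide alone. A QTc above 480 and up to 500 msec that persists after other QT-prolonging drugs are stopped has no specific eltrombopag rule.

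**3. Matching by dose step.** Section 8.1.2 halves every level: 200/2 = 100 mg and 300/2 = 150 mg. On that basis the 480 msec rule is missing at two of three East Asian steps (100 and 150 mg), and the ECGs at one (150 mg).

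**4. Matching by exposure.** Inputs are the exposure ratios r = 1.70 and 1.80 (Section 8.1.2) and 1.87 (Section 5.2.2, not adjusted for body weight). Assuming exposure proportional to dose, the standard-scale equivalent is East Asian dose × r.

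| East Asian dose | r = 1.70 | r = 1.80 | r = 1.87 | Against standard trigger |
|---|---|---|---|---|
| 100 mg | 170 | 180 | 187 | 0.85, 0.90, 0.94 of 200 mg |
| 150 mg | 255 | 270 | 280.5 | 1.28, 1.35, 1.40 of 200 mg; 0.85, 0.90, 0.94 of 300 mg |

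By exposure, then, the 480 msec rule is clearly missed at 150 mg. The 100 mg step falls a little short of the 200 mg trigger, and 150 mg a little short of the 300 mg trigger.

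**5. Sensitivity to proportionality.** Let AUC vary as dose^b. An East Asian dose d exceeds the exposure of a standard dose D when r × d^b > D^b, that is, when b < ln(r)/ln(D/d).

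- 150 mg against 200 mg: b < ln(r)/ln(200/150) = 1.84, 2.04, 2.18 for the three ratios.
- 100 mg against 200 mg, and 150 mg against 300 mg: b < ln(r)/ln(2) = 0.77, 0.85, 0.90.

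The 150 mg result for the 480 msec rule holds over a wide range of b, including proportionality (b = 1). The other two comparisons reach the trigger exposure only if exposure rises less than proportionally with dose.

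**The case against.** The strongest reply is that the literal reading is not the natural one. Section 8.1.2 introduces dose levels as paired values and uses the same term in the QTc rule shortly afterwards, so a site could read 200 mg as the second step. Section 5.1 also gives only the 100 mg starting dose with no intention of overriding the East Asian one. This is a fair account of what was probably meant. But Section 8.1.2 supplies the East Asian figure each time it sets a start, step or maximum, and the two QTc triggers do not. The text leaves the choice to sites. Figure 4, the dose-adjustment schema, is not available in the copy reviewed and could not be checked.

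Second, under proportionality only the 150 mg step exceeds a trigger exposure, and only the 200 mg one. That stands: the case for 100 mg in the exclusion and 150 mg in the ECG footnote rests on the protocol's own halving of doses, not on exposure.

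Third, the consequence is small. The eltrombopag safety section names no QT risk, no exposure-QT relationship is given, and few if any of at most 52 patients may be affected. The lenalidomide signal argues for wider ECG monitoring rather than for rescaling an eltrombopag trigger. All of this limits severity, but the protocol itself chose dose-triggered QTc rules.

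Fourth, rescaling leaves subjects at the second step under the 480 msec rule with no scheduled ECG. That is true, and it is equally true of non-East Asian subjects at 200 mg now. It is a separate gap that this correction does not close.

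**Conclusion.** The concern holds as a minor one. As written, the 480 msec exclusion and the on-treatment ECG schedule cannot apply to any subject on the East Asian dose scale. What is left uncovered is a persistent QTc above 480 and up to 500 msec, together with the scheduled ECGs that would help detect it or a value above 500 msec.

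The textual finding needs no assumption beyond reading the milligram values literally. Its extent (two steps without the exclusion, one without the ECGs) assumes matching by dose step. By exposure, the gap is clear only for the exclusion at 150 mg, equivalent to about 255 to 281 mg under assumed proportionality. The size of the subgroup is not given. Sample size and the primary efficacy analysis are unaffected.

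**What to change.** Use the protocol's halved scale in both places:

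- Section 8.1.2, QTc exclusion: after the 200 mg trigger, add *(100 mg and above in East Asian subjects)*.
- Section 2, footnote 12: after the 300 mg trigger, add *(150 mg in East Asian subjects)*.

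The first change adds no scheduled procedure, though a few more East Asian subjects at 100 or 150 mg may be excluded for QTc >480 msec. The second adds ECGs only for East Asian subjects who reach 150 mg. If the footnote's clock starts on reaching 150 mg, that is 5 visits (Day 1, Weeks 2, 4, 8 and 16) × 2 = 10 ECGs. If the 28-day column means every cycle, Week 12 is added: 6 × 2 = 12 through Week 16, then 2 per cycle. If the clock runs from the start of eltrombopag, two increases at 2-week intervals put 150 mg at Week 4 at the earliest. The count is then at most 3 × 2 = 6 (Weeks 4, 8 and 16), or 8 with Week 12.

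Under proportional exposure, both triggers would act in East Asian subjects at 85 to 94% of the exposure at which they act in others, which is slightly cautious.

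Whether to schedule ECGs from the second dose step for everyone is a separate decision, worth raising in the same amendment.

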8.2 SUPPORTIVE CARE

1. All supportive measures consistent with optimal patient care will be given throughout the study.

2. Therapies considered necessary for the patient's well being may be administered at the discretion of the Investigator. These therapies include antibiotics, analgesics, antihistamines, or other medications, and transfusions of red blood cells, platelets, or fresh frozen plasma given to assist in the management of complications associated with MDS or study treatment.

3. Packed RBCs: Transfusions of two units of packed RBCs should be considered for decline in hematocrit (HCT) to $< 25\%$ or symptoms of cardiovascular compromise. The following **transfusion thresholds and guidelines** are recommended for study participants: HCT $< 25\%$, two units of packed RBCs; HCT $< 21\%$, three units of packed RBCs; HCT $< 18\%$, four units of packed RBCs.

4 Platelets: Eight to ten units of random donor platelets or one cytopheresis unit of single donor platelets should be administered to all subjects with signs of hemostatic failure (i.e., bleeding or petechiae) or life threatening thrombocytopenia (i.e., platelet count $< 10,000/\mu\text{L}$).

5 Patients should not receive androgens or steroids for supportive treatment of their anemia or thrombocytopenia

6 Patients may receive hydrocortisone prophylactically to prevent transfusion reactions. Steroids given for adrenal failure, hormones administered for non-cancer related conditions (e.g. insulin for diabetes), and intermittent uses of dexamethasone as an antiemetic are permitted concomitantly with study drug. Short courses of steroids to treat study drug-induced skin rashes are also permitted.

8.3 DURATION OF THERAPY

Patients will receive protocol therapy unless:

1. Extraordinary Medical Circumstances: If at any time the constraints of this protocol are detrimental to the patient's health, protocol treatment should be discontinued
2. Patient withdraws consent.

3. Adverse event(s) (AEs) occur that, in the judgment of the Investigator, may cause severe or permanent harm or which rule out continuation of study drug.
4. Lack of therapeutic effect
5. Patient's disease converts to acute myeloid leukemia or disease progression.
6. Patient is lost to follow-up.
7. if a patient has a QTc >500 msec or QT >600 msec;
8. if a patient meets any of the following liver chemistry threshold criteria:
 ALT \geq 3xULN and bilirubin \geq 1.5xULN (>35% direct). ALT \geq 5xULN.

ALT \geq 3xULN if associated with the appearance or worsening of hepatitis symptoms or rash.

All subjects who discontinue study medication should continue to participate in the follow-up visits.

8.4 DURATION OF FOLLOW-UP

For this protocol, all patients, including those who discontinue protocol therapy early, will be followed for response until progression and for survival for 10 years from the date of registration. All patients must be followed through completion of protocol therapy.

8.5 CONCOMITANT MEDICATIONS AND NON-DRUG THERAPIES

Permitted Medications and Non-Drug Therapies

A reasonable effort will be made to document any medications the subject received within 30 days prior to Day 1. Any medication taken within 7 days of study medication administration must be recorded in the eCRF as a prior medication. All concomitant medications taken during the study will be recorded in the eCRF with indication, dose information, including any changes in dose, as well as start and stop dates and frequency of administration. The minimum requirement is that drug name, dose, and the dates of administration are to be recorded. If any medication is required at any time within 7 days before study medication administration until completion of last follow-up procedures, subjects should consult the investigator and details should be recorded in the eCRF.

Antacids, Cations and Vitamin/Mineral Supplements

Administration of eltrombopag with a polyvalent cation-containing antacid decreased plasma eltrombopag exposure by 70%, and a similar reduction was observed when eltrombopag was administered with a high-calcium meal. Therefore, every effort must be made to educate subjects on how to take study medication with medications or foods containing these polyvalent cations. Details of these and all concomitant medications should be recorded in the eCRF.

Eltrombopag should be taken on an empty stomach (1 hour before or 2 hours after a meal) or taken with food low in calcium (no dairy products). Allow at least a 4 hour interval between eltrombopag and other medications, foods, or products containing polyvalent cations (e.g. calcium, magnesium, aluminium, zinc, selenium or iron) such

as antacids, dairy products, and mineral supplements to avoid significant reduction in eltrombopag absorption due to chelation.

Antacids

Subjects requiring routine (e.g. daily) acid suppression should be encouraged to take H2 antagonists like ranitidine, famotidine or nizatidine, or proton pump inhibitors like omeprazole, esomeprazole or lansoprazole.

Subjects requiring occasional acid suppression may take liquid or chewable antacids (calcium carbonate, aluminum hydroxide or magnesium hydroxide), provided study medication is taken at least 4 hours before and 4 hours after consumption of cation-containing antacids.

Mineral Supplements and Dairy Products

Mineral supplements (such as calcium, magnesium, aluminium, zinc, selenium or iron) are permitted during the study but study medication must be taken at least 4 hours before and 4 hours after consumption of these supplements. Similarly, eltrombopag must be taken at least 4 hours before and 4 hours after consumption of dairy products (such as milk, yogurt, and cheese).

HMG-CoA Reductase Inhibitors (statins)

Subjects will be permitted to use HMG-CoA reductase (3-hydroxy-3-methyl-glutaryl-CoA) inhibitors during the study, but these drugs should be used with caution and a 50% dose reduction of the HMG-CoA reductase inhibitor is recommended, with close monitoring for safety, such as liver chemistry and signs and symptoms of myolysis, and efficacy, such as cholesterol and triglycerides (refer to individual product information for monitoring recommendations).

Preclinical data showed that eltrombopag is an inhibitor of the transporters OATP1B1 and BCRP. Therefore, a clinical drug interaction study to evaluate the impact of eltrombopag on the PK of rosuvastatin, an OATP1B1 and BCRP substrate, was conducted in healthy subjects. Co-administration of eltrombopag 75 mg once daily for 5 days with a single 10mg dose of rosuvastatin administered on Day 5 increased plasma rosuvastatin C_{max} 2.03-fold and AUC(0-∞) 55%. Concomitant administration of eltrombopag and other OATP1B1 or BCRP substrates should be used with caution.

Concomitant MDS Therapy

G-CSF is allowed during the study for subjects with severe neutropenia and recurrent infections. Subjects who enter the study on G-CSF should continue at the same dose schedule until the optimal dose of study medication has been established.

Any change in dosage of any concomitant medication (change in dose or frequency) MUST be recorded in the eCRF, to include: drug name, dose, frequency of administration, start and stop dates and indication.

Prohibited Medications and Non-Drug Therapies

Subjects must abstain from using prohibited prescription or non-prescription drugs within 7 days or 5 half-lives (whichever is longer) prior to the first dose of study

medication until completion of follow-up procedures (Section 5.3, Exclusion Criteria).

The following medications are prohibited during the study:

- Any other TPO-R agonists
- Treatment with deferasirox. Deferasirox shares some aspects of the safety profile of eltrombopag, and should therefore not be combined with eltrombopag to allow for a better identification of potential, eltrombopag-related events.
- Drugs that affect platelet function (including, but not limited to, aspirin, clopidogrel and/or NSAIDs) may also affect the results of the bleeding scale assessments during the study and are therefore prohibited. In the event their use is clinically indicated, those drugs will be permitted, but the subject(s) will be excluded from bleeding analyses.
- Anticoagulants (e.g. warfarin, heparin) may also affect results of the bleeding scale assessments during the study unless and therefore are prohibited. In the event their use is clinically indicated, those drugs will be permitted, but the subject(s) will be excluded from bleeding analyses.

